**Table 6-2 Dose Reduction**

Starting dose	Reduction level -1
3.0 mg FT-4101/placebo	1.5 mg FT-4101/placebo
4.5 mg FT-4101/placebo	3.0 mg FT-4101/placebo

## 7.0 STUDY POPULATION

### 7.1 Inclusion Criteria

Subjects who meet all applicable criteria at Screening will be included in the study:

1. Willing and able to give informed consent before any study-specific procedures being performed.
2. Male or female subjects  $\geq 18$  to  $\leq 75$  years.
3. Meets all of the following criteria:
  - a) CAP  $\geq 300$  dB/m by FibroScan® collected at screening or within 30 days prior to screening.

OR

Liver biopsy within 24 months, consistent with NASH (defined as the presence of steatosis, inflammation, and ballooning) with stage 2-3 fibrosis according to the NASH Clinical Research Network (CRN) classification (or equivalent).

Note criterion 3a must be met before evaluating 3b.
  - b) Screening MRI-PDFF with  $\geq 10\%$  steatosis.
4. Body mass index (BMI)  $> 25.0$  to  $< 45.0$  kg/m^2.
5. Stable body weight, defined as no weight gain or weight loss  $> 5\%$  over the previous 3 months.
6. Subjects with T2DM may also be included, if:
  - a) Subject with T2DM on stable doses of metformin monotherapy (subjects on combination therapy of metformin and sulfonylurea (SU) need to undergo washout period of 7 days of SU prior to dosing) with no changes in medication within the previous 6 months.
  - b) HbA1c  $< 9\%$  (one retest is permitted with the result of the last test being conclusive)
  - c) Fasting plasma glucose (FPG)  $< 240$  mg/dL ( $< 13.3$  mmol/L) (one retest is permitted with the result of the last test being conclusive)
7. Waist circumference  $\leq 57$  inches.
8. Female subjects must be non-pregnant and non-lactating.

Females may be surgically sterile, postmenopausal or of child-bearing potential. Females of childbearing potential must be using a highly effective method of birth control. See section [9.1.9](#) Contraception

Males must be surgically sterile, abstinent or if engaged in sexual relations of child-bearing potential, the subject and his partner must be using highly effective contraceptive methods. For details see section [9.1.9](#) Contraception.
9. Willing and able to comply with scheduled visits, drug administration plan, laboratory tests, other study procedures and study restrictions.

## 7.2 Exclusion Criteria

Subjects who meet any of the following criteria at Screening will be excluded from the study:

1. Type 1 diabetes and type 2 diabetic subjects on insulin therapy.
2. Diabetic complications, such as history of acute proliferative retinopathy.
3. Recurrent severe hypoglycemia (more than 1 event  $\leq$  6 month) or hypoglycemic unawareness or recent severe ketoacidosis (hospitalization  $\leq$  6 month), as judged by the Investigator.
4. Subjects with a history of, or active, chronic liver disease due to alcohol, autoimmune, primary biliary cholangitis, HIV, HBV or active HCV-infection, Wilson's,  $\alpha$ -1-antitrypsin deficiency, hemochromatosis, etc., and not due to NASH disease.
5. Any history of clinically significant or decompensated chronic liver disease including esophageal varices, ascites, encephalopathy or any hospitalization for treatment of chronic liver disease; or MELD score  $\geq$  10.
6. History of significant cirrhosis of the liver or FibroSure®  $> 0.75$  at Screening (as shown on the laboratory report under Fibrosis Score).
7. Alcohol consumption greater than 14 drinks per week for men or greater than 7 drinks per week for women and/or positive alcohol breath test. (One drink is defined as 12 fluid ounces of regular beer (5% alcohol), 5 fluid ounces of wine (12% alcohol), or 1.5 fluid ounces of 80 proof (40% alcohol) distilled spirits.)
8. Introduction of an anti-obesity drug in the past 6 months prior to screening.
9. History of gastrointestinal malabsorptive bariatric surgery any other gastrointestinal surgery that may induce malabsorption, history of bowel resection  $> 20$  cm, any malabsorption disorder, severe gastroparesis, any GI procedure for weight loss (including LAP-BAND®), as well as clinically significant gastrointestinal disorders (e.g. peptic ulcers, severe gastrointestinal reflux disease [GERD]) within less than 5 years.
10. Ingestion of drugs known to produce hepatic steatosis including corticosteroids, high-dose estrogens, methotrexate, tetracycline or amiodarone in the previous 6 months.
11. Ingestion of drugs (as listed in the Table Prohibited Medication) from time points specified until completion of the study.
12. History of, or current cardiac dysrhythmias and/or a history of cardiovascular disease event, including congestive heart failure (class C and D of the American Heart Association [AHA]), unstable coronary artery disease, myocardial infarction.

13. Significant systemic or major illnesses other than liver disease, including cerebrovascular disease, pulmonary disease, renal failure, organ transplantation, serious psychiatric disease, malignancy that, in the opinion of the investigator, would preclude treatment with FT-4101 and/or adequate follow up.
14. History of chronic skin and hair conditions such as psoriasis, eczema or any recurring rash/dermatitis requiring oral or topical corticosteroids or other topical applications within 12 months.
15. Hair loss or unexplained alopecia within 12 months.
16. History of chronic eye conditions, Sjögren syndrome or any history of dry eyes or allergic conjunctivitis requiring artificial tears or medicated eye drops or previous refractive surgery within 12 months (Subjects with dry eyes due to wearing contact lenses are eligible).
17. History of major depression, anxiety, suicidal behavior or attempts, or other unstable psychiatric disorders (within 2 years of screening), requiring medical treatment. (Subjects on stable antidepressants are allowed).
18. Uncontrolled hypertension, defined as systolic blood pressure  $>150$  mmHg and/or diastolic blood pressure  $\geq 100$  mmHg at screening (reading may be repeated on a different day). (Subjects with uncontrolled hypertension may be rescreened after 3 months, following initiation or adjustment of antihypertensive therapy).
19. Any device or other contraindication with the MRI examination, as per local imaging centers.
20. Ingestion of deuterated water within the previous 6 months.
21. Positive test for hepatitis B surface antigen (HBsAg), hepatitis C antibody (HCV Ab), or human immunodeficiency virus type 1 (HIV-1) or type 2 (HIV-2) antibody.
22. Abnormal laboratory results:
  - a) Alanine aminotransferase (ALT)  $> 5 \times$  upper limit of the normal range (ULN)
  - b) Total bilirubin  $> 1 \times$  ULN, except with diagnosis of Gilbert's syndrome
  - c) International normalized ratio (INR)  $> 1.2$  unless on anticoagulant therapy
  - d) Fasting Triglycerides  $> 300$  mg/dL
  - e) Platelet count  $< 100,000$  /mm^3
  - f) Abnormal kidney function test with glomerular filtration rate [GFR]  $< 60$  mL/min/1.73m^2 as estimated using the MDRD equation.
23. Participation in any other clinical interventional study receiving active treatment within the previous 30 days or 5 half-lives whichever is longer.
24. Have a known hypersensitivity to any of the ingredients or excipients of the study products.
25. Subject is unable to abstain from smoking during confinement periods.

26. History of illicit drug abuse as judged by the Investigator within approximately 1 year and positive test at Screening.
27. Clinically under the effect of marijuana at screening, as per Investigator evaluation.
28. Unwillingness to abstain from grapefruit (grapefruit containing food and beverages), star fruit (carambola), pomegranate, Seville orange and other food components that may interact with CYP3A4 from check-in throughout the entire course of the study.
29. Donation or loss of > 500 mL of blood or blood product within 56 days of dosing.
30. Any other condition which, in the opinion of the investigator would impede competence or compliance or possibly hinder completion of the study.

### 7.3 Study Restrictions/Precautions

#### 7.3.1 Prohibited Medications

Use of the agents listed below (prescription or nonprescription) is prohibited from the time points specified until completion of all study activities.

**Table 7-1 Prohibited Medications**

Medication or Class	Indication/Reason	From time point specified until the end of the study
Antihypertensive medication	Hypertension	Excluded unless on stable dose for at least 3 months prior to screening
Statins	Hyperlipidemia	Excluded unless on stable dose for at least 3 months prior to screening
Oral or systemic long-acting corticosteroids	E.g., chronic or acute non-infectious inflammatory conditions, auto-immune diseases	Within 3 months prior to screening
Antacids, anticholinergics, antispasmodics (e.g., modafinil, phenytoin), 5HT3 antagonists, dopamine antagonists, or opiates, antiemetics	Reduction/modification of GI motility	Within 2 weeks prior to screening
Orlistat, lorcaserin, sibutramine, etc., including over-the-counter and herbal supplements, or any medication with a labelled indication for weight loss or gain	Weight control treatment	Within 3 months prior to screening.

Medication that is a strong inducer or strong inhibitor of CYP3A4  Please see Appendix C in section 16.3 .	Interaction with CYP3A4	Within 15 days prior to dosing, unless half-life is greater than 72 hours, then it is prohibited for 5 half-lives prior to dosing.
--	-------------------------	--

### 7.3.2 Check-in Criteria

At check-in for any in-house period(s), a subject will not be allowed to check in if they meet any of the following criteria and the treatment period may be rescheduled one time. The Sponsor will be notified about the rescheduling in a timely manner.

1. Positive alcohol breath test.
2. Positive urine drug screen test.
3. Positive urine pregnancy test in female subjects. If sample is positive, blood sample will be sent to local lab for confirmation. A negative test result is mandatory prior to dosing.
4. Any medical condition that could interfere with the study, as judged by the Investigator.
5. Any use of disallowed concomitant medications within the last 24 hours.
6. Consumption of grapefruit (grapefruit containing food and beverages), star fruit (carambola), pomegranate, Seville orange and other food components that may interact with CYP3A4, within 24 hours prior to check-in.

### 7.3.3 Anticipated Risks

Normal precautions taken for a human study, including the provision of emergency equipment, will be taken during this study. Qualified and well-trained physicians and medical staff will instruct the subjects.

Possible anticipated, risks from the study procedure are outlined below:

#### 7.3.3.1 *IP related adverse events*

Dosing with the IP may have adverse effects on the skin (including alopecia) and eye. These effects were reversible upon dose interruption in previous studies. An assessment of hair loss at baseline and during the treatment cycles is recommended to adequately assess any potential AE of alopecia occurring during study participation. For further information, please see Norwood's Classification of Hair Loss in section [16.4](#), Savin's Pictorial Grading of Female Pattern Hair Loss in section [16.5](#) and the Investigator's Brochure (IB).

### *7.3.3.2 Deuterated Water adverse events*

The adverse effect reported with the intake of deuterated water is transient dizziness if the deuterated intake is more rapid than planned in this study. Dizziness typically resolves within 2-3 hours. Deuterated water has been given to humans for more than 70 years without problems. Animals have been raised for many generations on deuterated water, without any problems. No risks have been observed in studies examining the effect of deuterated water on male or female reproduction tissues, including sperm function.

### *7.3.3.3 Procedure related adverse events*

Study procedures involve the placement of a catheter which may lead to allergic reaction, redness, swelling, bruising, pain, bleeding or infection at catheter insertion site. The study procedures also involved the use of adhesive to secure the placement medical equipment. The adhesive may cause an allergic reaction, redness, swelling or itching when in contact with the skin.

### *7.3.3.4 Risks related to repeated blood draws*

Subjects will participate in several blood draws throughout the course of the study which have the potential to cause a venous line-vasovagal response, bruising, tenderness, and rarely infection.

## **8.0 STUDY MATERIALS**

### **8.1 Investigational Products**

#### **8.1.1 FT-4101**

FT-4101 is a potent, selective, orally bioavailable, small-molecule inhibitor of Fatty Acid Synthase (FASN). It is a non-hygroscopic, crystalline solid, obtained as polymorph Type B. FT-4101 capsules contain only drug substance filled into capsules with no other excipients. FT-4101 capsules will be provided in 3 different unit strengths for oral administration. For this study, the following doses may be used: 1.5 mg active capsules: Size 3 White/White opaque, 3 mg active capsules: Size 3 White/White opaque and 4.5 mg active capsules: Size 3 White/White opaque will be used.

#### **8.1.2 Placebo**

Placebo capsule is matching in size and color to all the active capsules. Placebo capsule contain Avicel PH102, an inert and stable compendial excipient, and will be provided by the Sponsor.

### **8.2 Other Medicinal Products**

#### **8.2.1 Deuterated Water**

Deuterated Water (70%) will be manufactured under cGMP conditions. Commercially available deuterated water will be provided by [REDACTED] from a qualified vendor.

Deuterated water will be provided as individual ready-to-use, single dose bottles each containing 50 mL of deuterated water (70 %).

### **8.3 Packaging, and Labeling of Products**

Each dose strength of FT-4101 and matching placebo are packaged in high-density polyethylene (HDPE) induction sealed bottles. For this study, 66 capsules are packaged per bottle.

The Sponsor will provide the Investigator with the labeled IP in accordance with specific country regulatory requirements.

The deuterated water will be packaged in individual ready-to-use single dosing bottle (e.g. the bottle can only be used once) each containing 50 mL of deuterated water and labeled with specific country regulatory requirements.

### **8.4 Storage and Drug Accountability of Products**

All clinical material must be kept in an appropriate, limited-access, secure location.

The investigational products (IP) and its storage instructions will be provided by the Sponsor. The IP FT-4101 must be stored securely at 15°C to 30°C.

The IP placebo must be stored at 15°C to 30°C.

The shipment of the IPs is recommended at 15°C to 25°C, packaged in a qualified shipper.

Individual bottles of deuterated water will be stored at room temperature (15°C to 30°C) according to instructions by the specific laboratory.

The IP will be shipped from the Sponsor to [REDACTED] drug depot. [REDACTED] will distribute the IP and deuterated water to each site.

The study staff is required to document the receipt, dispensing, and return/destruction of Study Products and supplies provided by or on behalf of the Sponsor.

Each study site may destroy IP or return deuterated water to drug depot per pharmacy manual's instructions after the close out visit.

The Investigator or Investigator's authorized staff must ensure the availability of proper storage conditions. The temperature of all study drugs will be monitored over 24 hours a day, 7 days a week (24/7). In case of incorrect storage, the Sponsor and monitor must be contacted without delay.

No study drugs may be dispensed to any person not enrolled in the study.

For further details please see the Pharmacy Manual.

## 8.5 Dose Regimen

The first dose of IP and deuterated water will be administered by qualified study staff while subjects are under observation in the clinical research unit. Accountability for deuterated water and IP will be performed to monitor compliance.

IP will be administered at t=0, orally with approximately 240 mL of water in the morning. Subjects do not need to be in a fasting state. A compliance check for the in-house dosing (hand and mouth check) will confirm that subjects have swallowed the complete dose. Actual time of dosing will be documented in the source documents and eCRFs.

During outpatient periods, subjects will take the IP at home once a day (QD) as instructed by study staff during the in-house period. Dosing will be intermittent, with 2 weeks of IP treatment and 1 week without any IP. Aim is to dose at approximately the same clock time on every dosing day.

Missed IP doses: Ideally, subjects should not miss more than 25% dosing days (>3 days) within 1 cycle. If more IP doses are missed than above, the PI will need to decide, with input from the Sponsor Medical Monitor, on whether the subject should be withdrawn from the study and replaced.

Details will be provided in the Operations Manual.

To maintain the double-blind aspect of the study, the investigational products will be prepared by unblinded staff that is not participating in investigational product

---

administration or interacting with study subjects in any other way. The study staff participating in other aspects of the study will be blinded to treatment.

**Table 8-1 Dosing Schedule for Treatment Cycles**

Cohorts	Number of Subjects	Treatment Schedule	Treatment-IP	No-IP	Treatment-IP	No-IP	Treatment-IP	No-IP	Treatment-IP	No-IP
			Cycle 1		Cycle 2		Cycle 3		Cycle 4	
Cohort A	N=10	Intermittent	FT-4101 3.0 mg QD Day 1-14	No IP Day 15-21	FT-4101 3.0 mg QD Day 1-14	No IP Day 15-21	FT-4101 3.0 mg QD Day 1-14	No IP Day 15-21	FT-4101 3.0 mg QD Day 1-14	No IP Day 15-21
	N=5	Intermittent	Matching Placebo QD Day 1-14	No IP Day 15-21	Matching Placebo QD Day 1-14	No IP Day 15-21	Matching Placebo QD Day 1-14	No IP Day 5-21	Matching Placebo QD Day 1-14	No IP Day 15-21
Cohort B	N=10	Intermittent	FT-4101 4.5 mg QD Day 1-14	No IP Day 15-21	FT-4101 4.5 mg QD Day 1-14	No IP Day 15-21	FT-4101 4.5 mg QD Day 1-14	No IP Day 15-21	FT-4101 4.5 mg QD Day 1-14	No IP Day 15-21
	N=5	Intermittent	Matching Placebo QD Day 1-14	No IP Day 15-21	Matching Placebo QD Day 1-14	No IP Day 15-21	Matching Placebo QD Day -14	No IP Day 15-21	Matching Placebo QD Day 1-14	No IP Day 15-21

### 8.5.1 Deuterated Water

Subjects will be instructed to drink 3 bottles of 50 mL of deuterated water (70%) daily on C1/D-14 through C1/D-8 and C4/D1 through C4/D7. Subjects will also be instructed to take each bottle of 50 mL of deuterated water at least 3 hours apart.

The first oral dose of deuterated water will be administered in-house in the morning of C1/D-14 and C4/D1 after Sebutape® and DNL blood sample collections. Subjects do not need to be in a fasting state. A compliance check for the in-house dosing will be performed. Actual time of dosing will be documented in the source documents and eCRFs. Subjects will then be instructed to continue the administration of deuterated water at home. The oral intake should occur at approximately the same time of day  $\pm$  3 hours on every dosing day. During the outpatient phase, subjects will fill in a log recording their daily deuterated water intake. If a dose is missed, it should be considered a “loss” and noted in the daily log and will be recorded in the CRF. Subjects must not double up on their intake (not take two doses at once).

If a deuterated water dose is missed, the subject should inform the study team and the team should record this information. There is no defined number of missed doses that constitutes non-compliance. Missed doses will be reported to the Sponsor Medical Monitor. The decision to withdraw a subject from study participation based on missed doses of deuterated water may be based on decision of the PI and the Sponsor Medical Monitor. If a subject is withdrawn, the subject can be replaced.

For more details please see the Operations Manual.

**Table 8-2 Dosing Schedule for Deuterated Water**

Cohorts	Subjects	Treatment Schedule	Treatment (7 days)	Treatment (7 days)
Cohort A	N=15	Daily	Deuterated Water TID 50 mL (at least three hours apart) C1/D-14 to C1/D-8	Deuterated Water TID 50 mL (at least 3 hours apart) C4/D1 to C4/D7
Cohort B	N=15	Daily	Deuterated Water TID 50 mL (at least three hours apart) C1/D-14 to C1/D-8	Deuterated Water TID 50 mL (at least three hours apart) C4/D1 to C4/D7

## 8.6 Overdose

If a study medication error occurs, it should be documented as Protocol Deviation. A brief description should be provided in the deviation, including whether the subject was symptomatic (list symptoms) or asymptomatic, and the event accidental or intentional.

Dosing details should be captured on the Dosing Case Report Form. If the subject takes a dose of Study Drug that exceeds protocol specifications and the subject is symptomatic, then the symptom(s) should be documented as an AE.

Should an overdose occur, the Investigator or designee should contact the Sponsor or designee within 24 hours of the investigator or qualified designee first becoming aware of the overdose.

## 8.7 Randomization and Blinding

Subjects will be randomized to the treatment according to an interactive web response system (IWRS). Randomization numbers will be generated from [REDACTED]. The IWRS will assign the next available randomization number at the time the site randomizes the subject, maintaining the 2:1 ratio (2 subjects on FT-4101 to 1 subject on placebo). Only authorized unblinded personnel will be able to see which treatment arm is assigned to a randomization number. Any replacement subjects will be randomized by IWRS to the same treatment arm that was assigned to the subject being replaced. The randomization number of the replaced subject will be incremented by 100 (e.g., subject [REDACTED] replaced with [REDACTED] subject [REDACTED] replaced with [REDACTED]).

## 8.8 Breaking of Blinded Code

The only persons with access to the treatment assignments during clinical conduct will be the designated pharmacy personnel who are responsible for the dispensing of study drug, the unblinded CRO operations team for investigational product accountability and serious adverse event (SAE) reporting, the unblinded statisticians who generate the randomization lists, and the bioanalyst for PK/PD samples. In general, the Sponsor Medical Monitor will remain blinded to treatment assignment. However, during the cohort safety review, if the decision is made to halt dose escalation due to an observed adverse event that potentially meets stopping criteria, the Sponsor Medical Monitor may be unblinded to that subject's data to ensure that the subject in question is indeed receiving FT-4101 and not placebo. This information will be conveyed via the unblinded statistician and will be limited to the subject with the safety issue of concern.

The code for a subject may be broken in a medical emergency, if knowing the identity of the treatment allocation would influence the treatment decision of the subject or if demanded by the subject. Unblinding will be done through the Electronic Data Capture (EDC), however if this is not available, the unblinded pharmacist at the site will have the subject list with treatment assignments, and as such would be able to break the blind in case of emergency. Whenever a code is broken, the person breaking the code must record the time, date, and reason as well as his/her initials in the source documents. During un-

blinding procedure in case of medical emergency, it should be ensured that no study personnel is unblinded to other subjects. Study site personnel and Sponsor personnel directly associated with the conduct of the study will not be unblinded.

If the study site needs to unblind a subject, the sponsor will, if possible, be contacted prior to breaking the blind. In all cases, the Study Monitor must be notified within 24 hours after emergency unblinding.

All codes (whether broken or not) must be kept throughout the trial period. Accountability of all broken or unbroken codes (hard copy or electronic) will be performed at or after trial closure and codes will be maintained in the Trial Investigator's File (TIF) at the site.

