**6.3 Rationale for Study Design and Endpoints**

This MAD study will assess the safety and tolerability, PK and preliminary PD of FT-4101 in overweight/obese subjects with NASH compared to placebo.

Two (2) cohorts will be assessed in ascending order, but may overlap, to determine the response to an intermittent dosing cycle (2 weeks of doing followed by 1 week off dosing).

Randomization is used to avoid bias introduced through an association between study drug allocation order and subject characteristics.

A double-blind design has been chosen to avoid bias and to maintain the blind between the administration of the study drug and placebo for subjects and clinical staff.

The placebo control group will control for changes in percent liver fat that may be caused by subjects' lifestyle and diet changes that may occur over the period of study participation.

Subjects with NASH will participate in the study, as these subjects are an important target population for FT-4101. Enrollment criteria will favor the target population. Percent liver fat will be determined by MRI-PDFF.

The proposed PK endpoints are well-established, commonly used parameters to characterize pharmacological profiles of drugs.

[figure not shown]
This is an exploratory study designed for proof of concept.

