**6.4 Dose Escalation**

Data from at least 12 subjects of Cohort A who have completed 2 of the 4 cycles of treatment (2 week on /1 week off) is required for safety review before dose escalation to Cohort B, provided no more than one subject had an early discontinuation suspected of being related to FT-4101. The safety and tolerability data will be reviewed and if deemed appropriate by the Safety Review Committee (SRC) consisting of the coordinating PI, the Sponsor medical monitor and at least 1 additional participating center PI, a dose escalation decision to proceed to Cohort B will be made that is based on the reviewed data. If there are no safety concerns, the next cohort may start and may partially overlap with the previous one.

The blind of the study will be maintained throughout.

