### 9.1.17.5 De Novo Lipogenesis (DNL) Assessment

Steady state contribution of fractional DNL to plasma triglyceride (TG) palmitate (representing hepatic DNL) and sebum fatty acids (e.g. palmitate and/or sapienic acid) will be determined using mass isotopomer distribution analysis (MIDA). For the assessment of fractional hepatic DNL during the study, subjects need to be in fasting conditions (no food or drink, except for water for 10 hours prior). Fasting is not required for the assessment of sebum DNL. A 2-week deuterated water labeling approach will be used to allow fully labeling of newly synthesized fatty acids (DNL) in liver triglycerides and sebum. Multiple blood and sebum samples will be collected throughout the assessment period for the measurement of deuterium enrichment in fatty acids and body water.

Sampling time points on different days should be at approximately the same clock time. For details please see the Operations Manual.

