#### **6.10.3.1. Change from Baseline in Fasting Hepatic De Novo Lipogenesis**

Multiple blood samples will be collected at C1D-11, C1D-7, and C1D1 and post-dose at C4D4, C4D8, C4D15, and C4D22 to measure deuterium enrichment in plasma body water and plasma triglyceride-palmitate. Fractional DNL will be determined by the quantification of newly synthesized palmitate through the DNL pathway in blood sampled in the fasting state after two weeks labeling period.

Fractional hepatic DNL (%) and its absolute and percentage changes from baseline will be summarized by visit and treatment group. P value from one-sided Wilcoxon-Mann-Whitney test at significance level of 0.05 will be provided. In addition, the change from C4D15 to C4D22 will be presented to evaluate rebound of DNL.

A MMRM model will be used to analyze the absolute change in fraction of fasting hepatic DNL from baseline; the model will include change in fraction of fasting hepatic DNL from baseline as dependent variable, treatment group as independent variable, baseline fraction of fasting hepatic DNL and visit and interaction term of treatment and visit as covariate, and a random slope and intercept per subject. Model parameters will be estimated using REML. An unstructured covariance matrix will be used to estimate the intercept-slope covariance. In case of convergence problem, other covariance structure will be used in the order of compound symmetry and variance component. The LS mean and standard error and its corresponding 90% confidence intervals and p-values will be presented for each post-baseline visit. The LS mean difference between treatment and placebo will be presented along with its 90% confidence interval and the p-value for each post-baseline visit. Similar SAS code as described in Section 6.10.2.1 will be used.

Line plots of the fraction of fasting hepatic DNL (mean  $\pm$  SD) will be plotted over time by treatment group for both pre-dose (C1D-11, C1D-7, and C1D1) and post-dose (C4D4, C4D8, C4D15, and C4D22); they will be overlaid to allow visual comparison.

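### Protocol 8.8 gives the PK/PD bioanalyst access to the treatment code, and nothing keeps the exploratory hepatic DNL and Sebutape assays blind

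*Protocol*

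**What the plan says.** Protocol 8.8 opens with a closed list: "The only persons with access to the treatment assignments during clinical conduct will be the designated pharmacy personnel", then the CRO team handling product accountability and SAE reporting, and finally "the unblinded statisticians who generate the randomization lists, and the bioanalyst for PK/PD samples". This is standing access during the trial. Emergency code-breaking is dealt with separately, later in the same section.

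Other sections describe the blind in general terms:

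- Protocol 6.3: "A double-blind design has been chosen to avoid bias and to maintain the blind between the administration of the study drug and placebo". The sentence goes on to name subjects and clinical staff as the people kept blind.
- Protocol 6.4, on dose escalation: "The blind of the study will be maintained throughout".
- Protocol 8.5, after describing the unblinded staff who prepare the product: "The study staff participating in other aspects of the study will be blinded to treatment".

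Protocol 9.1.17.3 and 9.1.17.5 make hepatic DNL, sebum DNL and sebum fatty acids laboratory measurements on blood and Sebutape samples, with DNL obtained by mass isotopomer distribution analysis (MIDA). SAP 6.10.3.1 then says of hepatic DNL: "P value from one-sided Wilcoxon-Mann-Whitney test at significance level of 0.05 will be provided". It adds an MMRM with a treatment-minus-placebo difference at each post-baseline visit.

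**The concern.** An assay analyst who knows arm and dose can, without intending it, treat samples differently when deciding whether to re-run one, how to process a signal, or whether to reject a result. The documents do not describe these steps; they are assumed here as ordinary features of such assays. If the choices differ by arm, the contrast with placebo is biased.

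At stake is mainly the hepatic DNL comparison. Protocol 4.1 states the clinical hypothesis as inhibition of DNL leading to less liver fat, so this endpoint is the trial's direct evidence of mechanism. If samples are assayed by someone holding the code, a reader of the results cannot rule out differential handling, and the doubt is hard to remove afterwards without re-assay.

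**Working it through.** This is mainly a check of the text. The plan gives no figure on the point.

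**1. Is the access limited anywhere?** Protocol 8.8 does not separate PK from PD assay and sets no time limit within conduct. Protocol 9.1.8, 9.1.16 and 9.1.17 leave sample details to the Laboratory and Operations Manuals. Protocol 11.1 has subjects and their biological material identified by unique numbers, but such numbers do not blind a person who holds the assignment list. The SAP says nothing about blinding of assays.

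**2. Does the analyst need the code?** The documents give no reason for either type of sample. For PK one can be inferred: SAP 4.3 restricts the PK set to FT-4101 recipients, so the code could spare placebo assays. Protocol 12.2.2, however, includes placebo subjects in the PK set, so even this is uncertain. For PD the inference is not available. The PD set includes placebo subjects (Protocol, Pharmacodynamic Set; SAP 4.5), and pooled placebo is the comparator (SAP 6.10), so every PD sample has to be assayed.

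**3. Which endpoints are exposed?**

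| Endpoint | Measured by | Analysis | Exposed? |
|---|---|---|---|
| MRI-PDFF | Central reader (Protocol 9.1.17.6) | Primary and secondary tests | No |
| ALT, AST, γGT, alkaline phosphatase, bilirubin | Central laboratory panel (Protocol 9.1.8) | MMRM | No |
| Total sebum | Sebumeter skin probe (Protocol 9.1.17.2) | Descriptive | No |
| Hepatic DNL | MIDA on blood samples | One-sided Wilcoxon test and MMRM (SAP 6.10.3.1) | Yes |
| Sebum DNL, sebum fatty acids | Sebutape samples | Descriptive (SAP 6.10.3.3) | Yes |
| Malonyl carnitine, other biomarkers | Laboratory performing the assay not clearly stated | Descriptive (SAP 6.10.3.4 and 6.10.3.5) | Only if this bioanalyst runs them |

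All the exposed endpoints are exploratory (Protocol 5.3, SAP 2.3).

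**4. How sensitive is the one test to sample handling?** The bias itself cannot be computed. What can be shown is how far a single rejected sample can move a test of this size. Inputs: 10 FT-4101 subjects at one dose and 10 pooled placebo subjects (Protocol 12.8), and no imputation of missing efficacy data (SAP 6.1.6), assumed to apply to DNL as well. Let U be the number of FT-4101/placebo pairs in which the FT-4101 value is the higher. Low U favours FT-4101, and p = P(U ≤ u) under the exact null distribution.

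- All samples kept, 10 v 10, U = 34: p = 0.124.
- Suppose the highest FT-4101 value lies above all 10 placebo values and is rejected. U falls to 34 − 10 = 24 with 9 v 10, and p = 0.047.

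Simulating with no treatment effect, the chance of p ≤ 0.05 is about 4% with all samples kept. It is about 10% if the least favourable FT-4101 sample is always dropped, and about 18% if the lowest placebo sample is always dropped as well. These are worst cases that assume systematic selection. They show sensitivity and do not estimate what would happen in this trial.

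**The case against.** Several stronger readings are tempting, and the documents do not support them.

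- **That 8.8 contradicts the double-blind design.** A reader might infer this from 6.3 if the sentence is cut short. In full it covers subjects and clinical staff, and a bioanalyst is neither. Sections 6.4 and 8.5 are general statements and do not mention laboratory analysts. The fair description is a gap in assessor blinding.
- **That the efficacy results are compromised.** The primary endpoint goes to a central reader and the secondary liver markers to the central laboratory. Neither passes through this bioanalyst.
- **That PD samples are in fact read with the arm known.** 8.8 grants access; it does not say the code is used during PD assay. Samples carry coded numbers, and the manuals, which are not available here, may require blind assay.
- **That the DNL result will be biased.** The assays are instrument-based, and the documents describe no step at which judgement enters. The arithmetic above assumes such a step.

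It can also be said that this is an exploratory proof-of-concept study, as Protocol 6.3 states, and that only one of the clearly exposed endpoints is tested. Both are correct and both reduce the weight of the point. What remains is that the governing document gives the code to the person named for the PD samples, with no visible safeguard and no stated need.

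**Conclusion.** The point holds as a limited gap. Protocol 8.8 gives the bioanalyst for PK/PD samples access to treatment assignments during conduct, and nothing in the Protocol or SAP keeps the PD assays blind. The exposed endpoints are hepatic DNL and the Sebutape measures, with other biomarkers included only if the same analyst runs them. The practical consequence falls on hepatic DNL, the only clearly exposed endpoint with p-values and a modelled contrast.

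The size and direction of any bias are unknown. The conclusion rests on two assumptions: that the manuals add no assay-level blinding, and that the assays leave some room for choices about individual samples. It is a worthwhile low-cost improvement and no threat to the primary analysis.

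**What to change.** In Protocol 8.8, narrow the last entry of the list to the bioanalyst for PK samples. Add a sentence there and in the laboratory manual: DNL and Sebutape samples, and any biomarker run by the same analyst, are assayed under the coded identifiers of Protocol 11.1 by staff without access to arm or dose until the PD results have been transferred and locked.

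If one analyst does both kinds of assay, withhold the code until the PD results are locked. That avoids a second analyst.

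The cost is one line in the protocol and one in the laboratory manual. With a single analyst, it also means either a later PK assay or assaying placebo PK samples that might otherwise have been skipped. No PD assays are added, because the placebo PD samples have to be run in any case.
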